**A study of lung ultrasound combined with
oxygenation index for precise extubation after
general anaesthesia in the elderly - a multicentre,
randomised, double-blind clinical trial**

Programme number: V4.0

Team leader: Tianjin First Central Hospital

Principal Investigator: [name]

Version date: 2022.11.4

Principal Investigator Programme Signature (Team Leader Unit)

Protocol name: Study of pulmonary ultrasound combined with oxygenation index for precise extubation after general anaesthesia in the elderly – a multicentre, randomised, double-blind parallel controlled clinical trial

Programme code: 20221104

Version number and date: 4.0, 4 November 2022

By signing this programme signature page, the investigator acknowledges and agrees that.

I have read the above research proposal and its annexes.

I agree to carry out the study in accordance with this study protocol and the ICH-GCP, local regulations and other applicable regulations to perform the relevant duties.

This document contains confidential information and will not be disclosed without written authorisation from the reporting party, except to those directly involved in the execution of the study or ethical/regulatory review.

I agree that I will ensure that all staff involved in this study are aware of their obligations in relation to the above commitments.

Research Unit: Tianjin First Central Hospital

[name]

Principal Investigator (in print) Principal Investigator (signature) Date of signature (year/month/day)

Programme Summary

Study Title	A study of lung ultrasound combined with oxygenation index for precise extubation after general anesthesia in the elderly - a multicenter, randomized, double-blind clinical trial.
Programme number	20221104
Version number and date	V4.0, 2022.11.04
Principal Investigator	Tianjin First Central Hospital, [name]
Senate Research Centre	5 tertiary hospitals
Purpose of the study	
Main research objectives
 
1. to evaluate the predictive value of LUS, MAPSE, TAPSE, DD and OI indicators for accurate postoperative extubation in elderly people undergoing general anaesthesia.
 
2. Explicit cardiac and pulmonary ultrasound combined with diaphragmatic mobility and oxygenation index is a good guide to cardiac and pulmonary complications after surgery in the elderly.

Study endpoints	The incidence of pulmonary complications at 7d postoperatively and mortality in patients at 30d postoperatively.
Study population	Elderly patients admitted to the PACU with a tube after major surgery under general anaesthesia, aged ≥ 65 years, expected to be mechanically ventilated for ≥ 3 h and who have passed the clinician's withdrawal screening test.
Study design	
We joined hands with the Fourth Central Hospital of Tianjin, the Fifth Central Hospital of Tianjin, the TEDA Hospital of Tianjin, the First Hospital of Shanxi Medical University and the Cancer Hospital of Shanxi Province to conduct a multicentre prospective clinical trial of 200 elderly patients, aged ≥ 65 years, after general anaesthetic surgery.
 
Ultrasound examinations of the heart and lungs were performed on elderly post-operative patients who had passed the SBT trial and needed to be extubated. LUS, MAPSE, TAPSE and DD were calculated, and arterial blood was drawn to determine OI using a blood gas analyser. The ROC curves of the combined predictors of LUS, MAPSE, TAPSE, DD and OI were plotted, the area under the curve (AUC) was calculated, the optimal threshold value was selected, the sensitivity and specificity were calculated, and the predictive value of the above indicators was evaluated.

General information and clinical indicators: for elderly patients admitted to the resuscitation room after general anaesthesia, record the patient's name, gender, age, pH at the end of the SBT test, $\text{PaO}_2/\text{FiO}_2$, PaO_2 , PaCO_2 , tidal volume.

222 The patient's heart rate, respiration, blood pressure, tidal volume and other parameters are recorded, as well as the patient's subjective response (presence or absence of dyspnoea). After extraction, another arterial blood gas is drawn and the arterial partial pressure of oxygen is analysed, as well as the inhalation oxygen concentration, respiratory rate and exhalation tidal volume. Calculate the oxygenation index (P/F value) = arterial partial pressure of oxygen (PaO_2)/inhaled oxygen concentration (FiO_2).

Withdrawal Screening Test (SBT).

(1) The cause of the mechanical ventilation has improved or been removed.

(2) Oxygenation indicators: oxygenation index $\geq 150 \sim 300$; PEEP $\leq 5 \sim 8 \text{ cmH}_2\text{O}$; $\text{FiO}_2 \leq 0.4$; $\text{pH} \geq 7.25$; for patients with COPD: $\text{pH} > 7.30$, $\text{FiO}_2 < 0.35$, $\text{PaO}_2 > 50 \text{ mmHg}$.

(3) Haemodynamic stability, absence of dynamic changes in myocardial ischaemia and absence of significant hypotension.

(4) The patient has the ability to breathe spontaneously and the respiratory centre is able to maintain a spontaneous respiratory rhythm.

Lung ultrasound tests.

At the end of the SBT, the same group of attending physicians with extensive ultrasound experience performed bedside ultrasound using a body-surface zone-based lung ultrasound scoring method according to the guidelines for the clinical application of critical care ultrasound published by the China Critical Care Ultrasound Research Group. A wide-frequency convex array probe was selected and the patient was placed in the supine position, and the anterior, lateral and posterior chest walls of both sides of the patient were examined using the 12-lung differentiation method.

LUS Rating:

(1) Normal ventilation zone: 0 points for lung sliding sign with A-line or < 3 separate B-lines; (2) Moderately reduced lung ventilation zone (B1): 1 point for multiple, typical B-lines; (3) Severely reduced lung ventilation zone (B2): 2 points for multiple fused B-lines.

(4) Pulmonary solid zone (C): tissue image with typical bronchial congestion, 3 marks.

The LUS score is the sum of the 12 regional lung scores, with each regional score being the most severe performance score for that region, measured over 5 min.

Transthoracic cardiac ultrasonography.

The patient's apical four-chamber view was obtained using M-mode ultrasound, with the M-mode ultrasound sampling line parallel to the septum as far as possible, and the sampling point located at the junctional tangent between the posterior mitral annulus and the left

ventricular free wall to obtain a clear image of the mitral annular motion displacement, freeze and magnify this image, and measure the maximum mitral annular displacement (MAPSE) from end-diastole to end-systole. In the same way, the M-mode ultrasound sampling line was placed parallel to the ventricular septum as far as possible, at which point the sampling point was located at the tangent of the junction between the anterior tricuspid annulus and the free wall of the right ventricle, and the maximum end-diastolic to end-systolic displacement (TAPSE) of the tricuspid annulus was measured. After three consecutive measurements, the mean of these two parameters is calculated and the difference between them is then calculated to give the difference in annular plane systolic excursion difference (APSED) between the mitral and tricuspid annuli. (The normal value for TAPSE is 22-24 mm; for MAPSE the normal value is ≥ 13 mm in men and ≥ 11 mm in women.)

Diaphragm mobility check:

The patient was placed in a supine position, with the chest and upper abdomen exposed. After stable breathing, an ultrasound convex array probe was used to detect under the rib arch in the right midclavicular line, and the distance between the diaphragm and the body probe was recorded in M ultrasound mode, and the difference between the diaphragm movement in the inspiratory and expiratory phases was measured at the end of the SBT test and recorded as DD.

The group was divided into a successful extraction group and a failed extraction group according to the outcome of the withdrawal.

The criteria for successful extubation are as follows: observe the withdrawal of extubation for 48 h. Signs of respiratory distress, i.e. increased respiratory rate (RR), increased heart rate (HR) and decreased oxygen saturation (SpO_2) within 48 h. The need for non-invasive mechanical ventilation or high-flow nasal cannula oxygen therapy or even reintubation is considered a failure of extubation, otherwise the extubation is considered successful.

The incidence of cardiac and pulmonary complications at 7d postoperatively and the mortality rate of patients at 30d postoperatively were recorded.

	
(1) Age ≥ 65 years, regardless of gender. (2) Post-tracheal intubation, ventilator-assisted ventilation. (3) Performing general anaesthetic surgery. (4) Duration of mechanical ventilation ≥ 3h. (5) Successfully passed the Spontaneous Breathing Test (SBT).

Exclusion criteria	
(1) Narrowing of the airway and compression of the airway. (2) Large breaks and burns to the skin of the chest. (3) Central respiratory failure. (4) Severe muscle weakness and absence of voluntary diaphragmatic activity. (5) Patients with unscheduled extubation. (6) Patients with combined end-stage cardiopulmonary disease.

Exit criteria	
Termination of the trial is required if the subject meets one or more of the following criteria.
 
 (1) Complications that endanger the life of the patient and require urgent resuscitation. (2) The subject or guardian requests to withdraw from the trial. (3) Other circumstances that, in the judgment of the investigator, warrant withdrawal from the trial.
Determination of sample size	
Two hundred subjects were to be enrolled in this study and divided into a successful extubation group and a failed extubation group according to the final extubation outcome. As there is no previous literature assessing the value of combined cardiopulmonary and diaphragmatic indicators to predict extubation, it was not possible to calculate a formal sample size, referring to previous literature examining the effect of single factors and the pre-trial main efficacy indicator of successful extubation, which was 70% for the conventional group and 100% for the pulmonary ultrasound group. The software PASS (version 21.0.3) was used to calculate that 166 patients were required for this trial at the 0.05 (one-sided) significance level. (taking into account a 10% shedding rate), which provides a 90% certainty test to obtain validity results for the test group compared to the conventional group.

Statistical analysis	
The general principles of descriptive statistical analysis in this study were as follows.
 
SPSS 22.0 was used for statistical analysis. Continuous measures were expressed as ($\bar{x} \pm s$) and tested for normality, and independent samples t-test was used for comparison of normally distributed data between the two groups. The χ^2 test was performed for statistical data to verify whether there was a statistical difference between the groups. $p < 0.05$ was statistically different.
 
Logistic regression model analysis was applied to derive prediction models for lung ultrasound score, diaphragm mobility and oxygenation index. ROC curves were plotted for lung ultrasound score, transthoracic cardiac ultrasound, diaphragm mobility, oxygenation index and the combined predictors, the area under the curve (AUC) was calculated for the subjects, the best cut-off value was selected, sensitivity and specificity were calculated and the predictive value of the above indicators was evaluated.

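### The randomised, parallel-controlled label and the 90% power claim describe a two-arm trial, but the protocol's methods describe one scanned cohort split by extubation outcome

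*Protocol*

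**What the plan says.** **Label.** The protocol name describes "a multicentre, randomised, double-blind parallel controlled clinical trial". The Study Title row also says randomised and double-blind.

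**Objective.** The first main objective, in the Purpose of the study row, is "to evaluate the predictive value of LUS, MAPSE, TAPSE, DD and OI indicators for accurate postoperative extubation".

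**Who is measured.** In the Study design row, heart and lung ultrasound is "performed on elderly post-operative patients who had passed the SBT trial and needed to be extubated", and arterial blood is drawn for the oxygenation index.

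**How groups arise.** The Study design row states: "The group was divided into a successful extraction group and a failed extraction group according to the outcome of the withdrawal". The Determination of sample size row repeats it: subjects are "divided into a successful extubation group and a failed extubation group according to the final extubation outcome".

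**Sample size.** The same row says that for the combined indicators "it was not possible to calculate a formal sample size". It then takes successful extubation of "70% for the conventional group and 100% for the pulmonary ultrasound group" and reports 166 patients at one-sided 0.05, allowing 10% shedding, with 90% power for the test arm against the conventional arm. Planned enrolment is 200.

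**Analysis.** The Statistical analysis row plans logistic prediction models, ROC curves with AUC, a best cut-off, sensitivity and specificity. It also plans a t-test between two groups and a chi-square test, without saying which groups.

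**The concern.** Two studies are described under one title. One has a conventional arm and an ultrasound arm and compares their success rates. The other measures everyone and asks how well the measurements predict extubation failure. The label and the power statement belong to the first; the objective, procedures, grouping rule and main analysis belong to the second.

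Two consequences follow. Readers, ethics committees and later meta-analysts would take a predictive cohort for randomised evidence. And 90% would be read as assurance for the ROC analysis, to which it has no connection. The precision of an AUC, a sensitivity or a specificity depends on how many patients fail and how many succeed, and the sample-size row says nothing about that for this cohort.

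The word double-blind is not part of the contradiction. Sonographers and outcome assessors can be blinded in a predictive-accuracy study, although the text does not say who is blinded to what.

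**Working it through.** **1. Do the arms exist in the design?**

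| Feature | Label and power statement | Methods as described |
|---|---|---|
| Groups | Ultrasound vs conventional | Successful vs failed extubation |
| How formed | Randomisation | Observed outcome |
| Who is scanned | One arm is implied | Patients who passed the breathing trial; no unscanned arm described |
| Question | Difference in success rates | Predictive value |
| Analysis | Two proportions | Logistic regression, ROC/AUC |

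The two outcome groups have success rates of 100% and 0% by definition. The 70% and 100% therefore cannot be theirs, and no other groups are defined.

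**2. Does the stated calculation reproduce?** Inputs from the sample-size row: p1 = 0.70, p2 = 1.00, one-sided alpha 0.05, power 0.90, dropout 10%. The allocation ratio is not stated; 1:1 is assumed.

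n per arm = [z(0.95)·√(2·p̄·(1−p̄)) + z(0.90)·√(p1(1−p1) + p2(1−p2))]² / (p2−p1)², with p̄ = 0.85

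= [1.645·√0.255 + 1.282·√0.21]² / 0.09 = 22.3, rounded up to 23.

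Total 46; 46/0.90 = 51.1, so 52 with dropout. Variants, all with dropout:

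- 1:1, one-sided with continuity correction: 65
- 1:1, two-sided: 63; with continuity correction: 76
- 1:1, exact Fisher: 56 one-sided, 65 two-sided
- largest over allocation ratios 1:1, 1:2, 1:3, 2:1 and 3:1, one- or two-sided, with or without correction: 102

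None gives 166. Conversely, 166 × 0.90 = 149.4, about 75 per arm, would have power above 99.9% for 70% vs 100%, not 90%.

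**3. What precision does the described design give?** The protocol gives no expected AUC and no failure rate for this cohort. Assumptions: AUC 0.80; failure rate 5% to 30%, where 30% is the complement of the conventional 70%; 200 × 0.90 = 180 evaluable. Hanley-McNeil, with n1 failures and n0 successes:

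SE² = [A(1−A) + (n1−1)(Q1−A²) + (n0−1)(Q2−A²)] / (n1·n0), where Q1 = A/(2−A) and Q2 = 2A²/(1+A).

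For A = 0.80, Q1−A² = 0.0267 and Q2−A² = 0.0711. With 9 failures: SE² = (0.16 + 8·0.0267 + 170·0.0711)/(9·171) = 0.0081, SE = 0.090, half-width 1.96 × 0.090 = 0.176.

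| Failure rate | Failures / successes | 95% half-width, AUC 0.80 | Sensitivity near 80%: Wilson 95% CI |
|---|---|---|---|
| 5% | 9 / 171 | 0.176 | 7/9: 45% to 94% |
| 10% | 18 / 162 | 0.126 | 14/18: 55% to 91% |
| 20% | 36 / 144 | 0.091 | 29/36: 65% to 90% |
| 30% | 54 / 126 | 0.077 | 43/54: 67% to 88% |

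Without shedding (N = 200) the half-widths are 0.167, 0.120, 0.087 and 0.073.

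**4. Side note.** Step 3 treats the marker and cut-off as fixed in advance. A simulation (3000 runs; five independent normal predictors of equal strength; true combined AUC 0.80; model and Youden cut-off fitted and evaluated in the same 180 patients) gave an apparent AUC above the fitted model's true AUC by 0.085 on average with 9 failures and by 0.023 with 54. The apparent Youden index was 0.63 against a true 0.34 with 9 failures, and 0.51 against 0.41 with 54.

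**The case against.** **Allocation details may sit in a statistical analysis plan or annex.** They may, but the protocol states twice that groups are formed by outcome. No later document can make those groups randomised.

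**The two groups in the Statistical analysis row could be arms.** That row names none, and the only two groups the design text constructs are the outcome groups. The fair request is to name them.

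**The sample-size row discloses its limits.** It does say that no formal calculation was possible for the combined indicators and that it borrowed from single-factor literature. That softens the fault, but the row still ends by asserting 90% power for a comparison this study does not make.

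**The size of the problem rests on assumed inputs.** This stands in part. The 5% failure rate has no source in the protocol, and the failure definition also counts non-invasive ventilation and high-flow oxygen, not only reintubation. At 30%, the one rate derivable from the text, the AUC half-width is a moderate 0.077. The 180 is also an inference, since the protocol applies its 10% in reaching 166, not to 200. The side note in the working concerns model validation and would apply under a correct title too; its five predictors are one reading, as the analysis row lists three for the logistic models. The verdict does not rest on it.

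**The predictive question remains answerable.** True. The label and power claim change no measurement and no planned ROC analysis. The harm is misdescription and false assurance.

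**Conclusion.** The point holds, and the protocol must be corrected. Its design label and its only power figure both describe a two-arm contrast that the methods do not contain. This follows from the text alone and needs no assumption.

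The power statement also fails arithmetically: its inputs give 23 per arm, or 52 in total with dropout at 1:1, and at most 102 under any variant tried, against 166 stated.

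The precision the study can expect is undetermined until a failure rate is given. For an AUC of 0.80 and 180 evaluable patients, the half-width varies more than twofold, from 0.176 to 0.077, as failures run from 5% to 30%. Those figures depend on the stated assumptions and are optimistic for a combined model and cut-off chosen in the same data.

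**What to change.** Reconcile the title, protocol name, and the Study Title, Study design, sample-size and analysis rows. If the methods stand:

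1. Relabel the study a multicentre prospective predictive-accuracy cohort wherever the title appears, and remove randomised and parallel controlled. Keep double-blind only if the sponsor can state who is blinded to what.
2. Withdraw the two-arm power claim and state precision instead. Draft wording: *Of 200 enrolled, about 180 are expected to be evaluable after 10% shedding. With an assumed extubation failure rate of 5% to 30% (9 to 54 failures) and an AUC of 0.80, the 95% CI half-width is about 0.18 to 0.08. This is for a fixed marker and is optimistic for a combined model and cut-off chosen in the same data.* Replace the assumed range with an expected failure rate and its source.
3. Name the groups in the t-test and chi-square test, and limit conclusions to predictive performance. As a related edit, reconcile the Study endpoints row, which reads "The incidence of pulmonary complications at 7d postoperatively and mortality in patients at 30d postoperatively", with extubation failure as the outcome being predicted.

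If a randomised comparison is intended, write the arms, the allocation and an analysis by arm into the design.

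**Cost.** The first route is a text amendment with no new data collection. It gives up a more favourable design label and the 90% figure, and 200 may have to change if the stated precision is judged too low at the expected failure rate. The randomised route is a new design and much costlier.

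### The 48 h extubation rule, the reference label for the ROC analyses, does not say whether distress signs alone are failure and does not classify death or exit within 48 h

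*Protocol*

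**What the plan says.** The rule stands in the protocol's Programme Summary, Study design, under the criteria for successful extubation. It has four parts.

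- A window: "observe the withdrawal of extubation for 48 h".
- A list without a predicate: "Signs of respiratory distress, i.e. increased respiratory rate (RR), increased heart rate (HR) and decreased oxygen saturation (SpO_2) within 48 h".
- A verdict: "The need for non-invasive mechanical ventilation or high-flow nasal cannula oxygen therapy or even reintubation is considered a failure of extubation".
- A residual clause: "otherwise the extubation is considered successful".

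Death is not named in the rule. It appears separately in the next paragraph, where "the mortality rate of patients at 30d postoperatively were recorded". The Exit criteria end participation for, among other things, "Complications that endanger the life of the patient and require urgent resuscitation", and do not say which outcome group such a patient joins.

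Study design and Determination of sample size both form the two comparison groups from this outcome. Statistical analysis then plans ROC curves, AUC, best cut-off, sensitivity and specificity for each index and for the combination.

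**The concern.** A reference standard has to give the same label to the same patient at every hospital. This one leaves two matters open.

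First, the paragraph is introduced as the criteria for success, then lists signs of distress without saying what follows from them. One site may count the signs as failure in themselves. Another may treat them as what is watched for, with only the need for support counting. Neither site contradicts the text. On the first reading, no size, duration or comparison value says when a sign is present.

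Second, the residual clause puts everyone not named as a failure into the success group. Read literally, that includes a patient who dies within the window without a need for support. A patient who exits early has no stated label.

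At stake is main objective 1, the predictive value of the ultrasound and oxygenation indices. If sites read the rule differently, the label differs by site, and later analysis can repair that only if the components were captured separately. This is not a detail left to the SAP, because the protocol itself fixes the rule.

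**Working it through.** **Step 1. Apply the rule to the same patients under both readings.** Reading A: signs alone are failure. Reading B: only the need for support is failure.

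| Patient, within 48 h | Reading A | Reading B |
|---|---|---|
| All three signs, no need for support, survives | failure | success |
| Needs support, receives it | failure | failure |
| Needs support, declines it, dies | failure | failure |
| Shows the signs, no need for support, dies | failure | success |
| No signs, no need for support, dies | success | success |
| Exits for a life-threatening complication | not stated | not stated |

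Rows 1 and 4 depend on the reading. Row 5 is a success under both unless the exit criterion removes the patient. Row 6 is open under both: a patient reintubated in an emergency can meet both the failure rule and the exit criterion.

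**Step 2. How many labels could the signs move?** The protocol gives no frequency for the signs, so there is no figure of its own to reproduce here. The assumption is that each sign occurs in a proportion p = 0.30 to 0.60 of patients, independently. The text joins the signs with 'and', so all three are required:

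- p³ = 0.30³ = 0.027; × 200 = 5.4, about 5 patients
- p³ = 0.60³ = 0.216; × 200 = 43.2, about 43 patients

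Reading A thus labels 2.7-21.6% as failures through signs, and reading B none. Some of these patients would also need support and be failures anyway, so the net difference is at most this.

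**Step 3. What could that do to an AUC?** This is an illustration on assumed values: 200 patients, 20 true failures (10%), true AUC 0.85, reading B taken as the truth, and labelling errors unrelated to the predictors. With PPV and NPV the predictive values of the failure and success labels,

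AUC observed = 0.5 + (AUC − 0.5) × (PPV + NPV − 1).

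If a fraction of the 180 true successes is labelled failure, NPV stays 1:

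- 5% (9 patients): PPV = 20/29 = 0.69; AUC = 0.5 + 0.35 × 0.690 = 0.74
- 10% (18 patients): PPV = 20/38 = 0.53; AUC = 0.5 + 0.35 × 0.526 = 0.68
- 20% (36 patients): PPV = 20/56 = 0.36; AUC = 0.5 + 0.35 × 0.357 = 0.63

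At 10% mislabelled, varying the true failure rate from 5% to 30% gives 0.62 to 0.78.

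**Step 4. What could missed deaths do?** Now label 5% or 10% of true failures as successes, with PPV = 1:

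- 20 true failures, 1 missed: NPV = 180/181 = 0.994; AUC = 0.848
- 20 true failures, 2 missed: NPV = 180/182 = 0.989; AUC = 0.846
- 60 true failures (30%), 3 or 6 missed: NPV = 140/143 or 140/146; AUC = 0.843 or 0.836

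The effect on the AUC is small throughout.

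**The case against.** The strongest reply is that the rule is clear enough. Only the need for support carries a verdict, so the signs are simply what is observed. The planning assumption supports this: "successful extubation, which was 70% for the conventional group and 100% for the pulmonary ultrasound group". A 100% success rate sits poorly with failure on vital signs alone. This makes the support-only reading the more natural one, but nothing in the paragraph excludes the other, and a site has only the paragraph to go by.

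A reader might infer that a change of any size in any one sign is failure. Under the Step 2 assumptions that would give 1 − (1 − p)³ = 66-94%, or 131-187 of 200. The documents do not support it: the text says 'and', and it describes signs of respiratory distress, not any postoperative change. Independence is also doubtful for three signs of one condition, so even 3-22% is only a range under stated assumptions.

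A reader might also infer that every patient who dies without receiving support is a success. That goes too far. The criterion is the need for support, so declined support is already failure. An arrest requiring resuscitation may fall under the exit criterion. If signs count, a patient who shows them before dying is a failure. The gap is therefore narrow. That 30-day mortality is recorded is true, but nothing carries an early death back into the 48 h label.

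Finally, Step 3 assumes errors unrelated to the predictors. Patients with real distress signs may well have worse ultrasound values, and the loss would then be smaller. If signs alone were regarded as true failure, the error would run the other way.

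**Conclusion.** The point holds as an ambiguity and a gap in the reference outcome. It does not show that the rule misclassifies patients in both directions as a matter of fact: the two error directions rest partly on opposite readings.

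Three things are established from the text alone. The rule does not say whether distress signs alone are failure, and gives no criteria for them. Its residual clause makes a success of a death within 48 h without a need for support (and, if signs count, without signs). The label after an exit within 48 h is not stated.

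The size is conditional. With each sign in 30-60% of patients independently and all three required, the readings differ by up to 5-43 of 200 labels. In the illustration, mislabelling of 5-20% of successes takes an assumed AUC of 0.85 to between 0.74 and 0.63. Missed deaths leave it at 0.836-0.848, so for deaths the case rests on validity and not on numerical impact.

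**What to change.** Reconcile the Study design and Exit criteria text into one outcome rule that every hospital applies:

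- Keep the existing criterion of need for non-invasive ventilation, high-flow oxygen or reintubation.
- State whether distress signs alone count as failure. If they do, the protocol must state the criteria. If not, record them only as the reason for support.
- Count death from any cause within 48 h as not successful.
- Classify patients who exit within 48 h for a life-threatening complication by the same rule, neither dropping them nor making them successes by default.
- Record each component (signs, need for each kind of support, death, exit) separately in the case report form, so that the label can be rebuilt and checked.

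The cost is a few sentences in the protocol and one or two case report form fields. The number of patients labelled as failures may shift.

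### The sample size of 166 does not follow from its stated inputs, the 200 is unexplained, and the calculation is for a two-arm comparison that the described cohort does not contain

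*Protocol*

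**What the plan says.** The Programme Summary, under Determination of sample size, begins with the enrolment figure: "Two hundred subjects were to be enrolled in this study". It says these subjects will be divided by extubation outcome, and that no formal calculation was possible because the combined indicators had not been studied before. It then reports a formal calculation: "The software PASS (version 21.0.3) was used to calculate that 166 patients were required for this trial at the 0.05 (one-sided) significance level". The effect size is the rate of successful extubation, "which was 70% for the conventional group and 100% for the pulmonary ultrasound group". A 10% dropout rate is said to be already included, and the stated assurance is 90% to "obtain validity results for the test group compared to the conventional group". No test, allocation ratio or margin is named, and no step leads from 166 to 200.

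The protocol name on the signature page calls the study "a multicentre, randomised, double-blind parallel controlled clinical trial". The Study design section describes something else: "Ultrasound examinations of the heart and lungs were performed on elderly post-operative patients who had passed the SBT trial", and later "The group was divided into a successful extraction group and a failed extraction group according to the outcome of the withdrawal". The Statistical analysis section plans logistic regression and ROC curves, in which "the area under the curve (AUC) was calculated for the subjects, the best cut-off value was selected", together with t-tests and chi-square tests between two groups.

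**The concern.** Three things in the sample-size section do not fit together.

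- A difference of 30 percentage points with one rate at 100% is very large, so 166 looks far too many for 90% power.
- Enrolment is set at 200 without a reason, although the calculated number already allows for dropout.
- The calculation needs a conventional arm and an ultrasound arm. Outside the sample-size section no such arms are described.

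What is at stake is the study's only quantitative justification. The study as described estimates an AUC, a cut-off, sensitivity and specificity. The precision of the AUC and sensitivity depends mainly on how many extubations fail, and the sample-size section does not consider that number. A reader cannot tell from it what 200 patients can show.

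**Working it through.** **Inputs from the sample-size section.** p1 = 0.70, p2 = 1.00, difference d = 0.30; one-sided alpha 0.05 (z = 1.645); power 0.90 (z = 1.282); 10% dropout. Assumed, because not stated: 1:1 allocation and no margin.

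**Step 1: attempt to reproduce 166.**

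- Pooled z-test: n = [1.645 × √(2 × 0.85 × 0.15) + 1.282 × √(0.70 × 0.30 + 0)]² / 0.30² = 22.3, so 23 per group.
- Continuity-corrected: n = (22.3/4) × [1 + √(1 + 4/(22.3 × 0.30))]² = 28.6, so 29 per group.
- Fisher's exact test, by enumeration: power 0.889 at 24 per group and 0.910 at 25, so 25 per group.
- Unpooled z-test: n = (1.645 + 1.282)² × 0.21/0.09 = 19.98, so 20 per group.

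| Test (one-sided) | Per group | Total | Total / 0.9 |
|---|---|---|---|
| Unpooled z | 20 | 40 | 45 |
| Pooled z | 23 | 46 | 52 |
| Fisher exact | 25 | 50 | 56 |
| Continuity-corrected | 29 | 58 | 65 |
| **Protocol** | – | – | **166** |

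Two-sided testing gives 28 (pooled) or 34 (continuity-corrected) per group, or 63 to 76 in total with dropout. Across allocation ratios from 1:4 to 4:1, the largest z-test total, pooled or continuity-corrected, is 95 one-sided or 117 two-sided. None is near 166.

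**Step 2: what power the stated size would give.** At 75 per group (about 166 × 0.9 = 149 evaluable), Fisher power for 70% versus 100% is 1 minus about 10⁻⁷. The pooled normal approximation gives 0.99994.

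**Step 3: what would produce about 166.** Each route needs an input that is absent or different from the one stated.

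- A superiority margin of 0.145: (1.645 + 1.282)² × 0.21/0.155² = 74.9, so 75 per group, and 150/0.9 gives 167.
- A test-group rate of about 89% in place of 100%: 169 with dropout (pooled, one-sided).
- Extreme allocation of 149 evaluable patients: Fisher power is 0.887 at 11:138 and 0.915 at 12:137 (conventional:ultrasound), and 0.902 at 138:11. The pooled approximation gives 0.903 at 7:142, but it is weak with 7 patients.

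**Step 4: the step from 166 to 200.** Dropout is already in the 166. Applying it a second time gives 166/0.9 = 185, not 200.

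**Step 5: what 200 offers the analysis described.** Assume 10% of the 200 are lost, leaving 180. A 30% failure rate follows from the stated 70% conventional success; 10% and 5% are assumptions.

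For the AUC (A), with f failures and s successes, the Hanley–McNeil variance is [A(1−A) + (f−1)(Q₁−A²) + (s−1)(Q₂−A²)]/(f·s), where Q₁ = A/(2−A) and Q₂ = 2A²/(1+A). At A = 0.80, Q₁ = 0.667 and Q₂ = 0.711. With f = 54 and s = 126, the variance is (0.16 + 53 × 0.0267 + 125 × 0.0711)/6804 = 0.00154, and 1.96 × SE = 0.077. The half-widths for sensitivity and specificity are 1.96 × √(0.8 × 0.2/n), with n = f and n = s respectively.

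| Failures : successes | AUC, true 0.80 | Sensitivity, true 0.80 | Specificity, true 0.80 |
|---|---|---|---|
| 54 : 126 (30%) | ±0.077 | ±0.11 | ±0.07 |
| 18 : 162 (10%) | ±0.126 | ±0.18 | ±0.06 |
| 9 : 171 (5%) | ±0.176 | ±0.26 | ±0.06 |

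The value 0.80 is itself an assumption. By the same formula, a true AUC of 0.70 gives ±0.088, ±0.140 and ±0.195 for the three rows; a true AUC of 0.90 gives ±0.058, ±0.097 and ±0.136.

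**Step 6: the groups.** The sample-size calculation compares success rates between two assigned groups. The only groups that the procedures define are those who were successfully extubated and those who were not. Success rates cannot be compared between groups defined by success. The planned t-tests and chi-square tests can therefore refer only to the outcome groups and do not supply the missing arms.

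**The case against.** The strongest reply has four parts.

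- The protocol partly discloses the problem. It admits that no formal calculation was possible for the combined indicators and that it borrowed from single-factor work. This stands as context, but it does not help: the same section then states a software result and a 90% assurance as if they applied to this trial.
- The error is in the safe direction. For the comparison named, 166 is well over twice what is needed, and enrolling more than a calculated minimum is common. This stands for the two-arm comparison, and the unexplained 200 taken alone would be a minor reporting gap. It gives no comfort for the ROC analysis, for which no requirement was calculated.
- At the only failure rate the protocol implies (30%), precision for the AUC is reasonable. The poor figures rest on assumed rates of 10% and 5% and an assumed true value of 0.80. This is fair, and the figures are shown as a range for that reason. That rate also comes from a conventional group the described study does not contain.
- The software may have been given a margin or another allocation. That is possible, but neither is stated, so the number cannot be traced.

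The unpooled z-test widens the one-sided range downward to 45, further from 166.

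**Conclusion.** The concern holds. The stated inputs give 52 to 65 patients with 10% dropout (45 with an unpooled test, 63 to 76 with the pooled or continuity-corrected test if two-sided) against a stated 166, assuming 1:1 allocation and no margin. At 1:1 the stated size would give power above 99.9% for 70% versus 100%, not 90%. The 200 is not derived from anything. The calculation belongs to a two-arm comparison that appears only in the sample-size section and in the protocol's description of itself as randomised and parallel controlled; the procedures and analysis describe a single cohort. The arithmetic does not show that 200 is too few. It shows that the protocol gives no basis for judging, and that AUC precision could range from about ±0.08 to ±0.18 at a true AUC of 0.80, depending on a failure rate the plan does not consider. This must be fixed.

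**What to change.** First settle the design: reconcile the randomised, double-blind, parallel-controlled label with the single cohort in the Study design and Statistical analysis sections.

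- **If the cohort is confirmed:** remove the 166 and the 90% power statement. Keep 200 as the planned enrolment. Restate its basis as the expected 95% confidence interval half-widths for AUC, sensitivity and specificity over an assumed range of failure rates, for example 5% to 30%. Set a precision target and say whether 200 meets it across that range. Without a target, do not call 200 adequate.
- **If two arms are intended:** describe the arms and how patients are assigned, and state the test, rates, margin, allocation, power and dropout so that together they reproduce the number.

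The cost for the cohort route is one rewritten paragraph once the design is clear. The stated assurance will look less favourable if failures are rare, and 200 may prove too few at the low end of the range.
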